All PAH AH patients will be diagnosed and medically managed by liver disease specialists (Hepatologists CI [name] and CI [name]) and Addiction specialist (CI [name]). Liver biopsy remains the gold standard for diagnosis ([name], et al., 2011), however indications for physician practice varies. While biopsy is the preferred inclusion criterion, absence will not be an exclusion criterion. For patients without liver biopsy, inclusion requires 1). Consistent alcohol risk history, 2). Absence of other acute liver injury risk; 3) at least 2/3 of:

jaundice < 8 weeks, AST/ALT ratio > 2; neutrophilia. Further characterised on AH severity (Maddrey Discriminant Function 32) and the presence of cirrhosis.

SAMPLE SIZE AND STATISTICAL OR POWER ISSUES

To determine non-inferiority or superiority of the new treatment protocol when the primary outcome is patient retention non-inferiority requirements were calculated in R version 3.5.0. Holding power level at 80% and alpha at 0.05, with a present response rate for patients with AH completing treatment at 30% and a modest protocol goal of 40%, a sample size of 70 patients is required to support non-inferiority within a 10% equivalence margin. Given that we have historical data for $N \sim 130$ patients, we only require 35 ($70 / 2 = 35$) patients to commence the new protocol for this study to be sufficiently powered.

METHODOLOGICAL APPROACH

AIM 1: ASSESSMENT OF TREATMENT PROTOCOL

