Assessment of alcohol use and dependence severity include the following comprehensively validated self-report measures: Brief Michigan Alcoholism Screening Test (bMAST), Alcohol Use Disorders Identification Test (AUDIT), Timeline Follow-back Procedure (TLFB), Severity of Alcohol Dependence Questionnaire (SADQ), and the Mini Alcohol Craving Experience scale (MACE). Alcohol related psychological constructs are assessed by the Drinking Expectancy Profile (DEP; outcome expectancies and refusal self-efficacy), Motivation Thought Frequency Scale (MTF; abstinence motivation), and Dysfunctional Impulsivity Scale (DIS). Social factors are examined by the Perceived Support Scale and routine assessment of demographic information. Liver disease severity will determined by MELD score. Neurocognitive functioning are assessed by the Trails A&B. Quality of Life are assessed by the Chronic Liver Disease Questionnaire (CLDQ), Short Form-6D, Depression Anxiety,

Stress Scale (DASS-21) and General Health Questionnaire (GHQ). Blood samples are taken for full medical work up as part of routine care.

RATIONALE FOR CHOICES OF METHOD/S (TIED TO PROJECT AIMS/OBJECTIVES)

As this is foremost a service improvement and quality assurance exercise, data collected will be compared to historical controls to ensure all patients receive the best available care.

TIMEFRAMES

Based on historical trends recruitment and treatment of the required 50 AH patients will take approximately 2-years from commencement of the study. Analysis of the available data and any publication is expected to be completed within 2-years following patient intervention.

PATIENT CONSENT

In standard care each patient signs a consent form agreeing that "I understand that deidentified data (anonymous data) collected may be used for program evaluation" as well as consent to participate in the program. Consistent with recent National Statement on Ethical Conduct in Human Research updates we include an 'opt-out' option at multiple points of the program.

Regarding the updated protocol and collection of genetic material, patients are verbally informed of the protocols and purpose surrounding saliva collection and provided an information sheet and consent form specifically outlining this information (attached). Patients are provided time to read the consent form and invited to ask any questions. Patients may provide or withdraw consent at any time. Provision of consent does not alter patient care in any way.

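### The protocol's inputs give 70 patients per group, so halving 70 to 35 leaves about 70% power at one-sided 0.05 rather than 80%, and the target of 35 is not reconciled with the 50 given under Timeframes.

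*Protocol*

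**What the plan says.** The only power calculation is in the Protocol, section Sample Size and Statistical or Power Issues. It fixes the error rates with "Holding power level at 80% and alpha at 0.05", without saying whether alpha is one- or two-sided. Completion of treatment is taken as 30% now and 40% under the new protocol. From these it concludes that "a sample size of 70 patients is required to support non-inferiority within a 10% equivalence margin". The 70 is not labelled as per group or as a total.

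The roughly 130 historical patients are then given as the reason for a smaller new group: "we only require 35 ($70 / 2 = 35$) patients to commence the new protocol for this study to be sufficiently powered".

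The Timeframes section states a different requirement: "recruitment and treatment of the required 50 AH patients will take approximately 2-years from commencement of the study". No text connects 35 to 50, whether by a dropout allowance, a recruited-versus-commencing distinction or a separate need for Aim 2. The Data Analysis section refers back to this one power statement and adds no other.

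**The concern.** Halving 70 is correct only if 70 is the total for two equal groups. If it is the size of each group, the new-protocol group has been cut to half of what the calculation asked for. A historical group larger than 70 can offset part of that cut, but the protocol does not show that it offsets all of it.

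At stake is the claim that the primary comparison is adequately powered. If 35 were the number analysed and the 10-point gain were real, the non-inferiority test would fail about 30% of the time, not the 20% that the protocol declares. A second, smaller problem is that a reader cannot tell whether the target is 35 or 50, or whether both count the same patients.

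**Working it through.** **Inputs** (Protocol, sample size section): p_old = 0.30, p_new = 0.40, margin = 0.10, power = 80% (z = 0.842), alpha = 0.05 with sidedness not stated (z = 1.645 one-sided 0.05; 1.960 one-sided 0.025), historical n about 130, new n = 35. From Timeframes: new n = 50.

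**Step 1: reproduce the 70.** For non-inferiority of two proportions, the distance from the margin is 0.40 − 0.30 + 0.10 = 0.20 and the variance sum is 0.30×0.70 + 0.40×0.60 = 0.21 + 0.24 = 0.45.

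n per group = (z_alpha + z_power)² × 0.45 / 0.20²

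- One-sided 0.05: (1.645 + 0.842)² × 0.45 / 0.04 = 69.6, so **70 per group**, 140 in total.
- One-sided 0.025: 88.3, so 89 per group.

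Other variants do not give 70 as a total either:

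- pooled variance at one-sided 0.05: 70.3 per group;
- no true difference at one-sided 0.05: 260 (both rates 30%) to 297 (both 40%) per group;
- superiority of 40% over 30%: 281 (one-sided) or 356 (two-sided) per group;
- one-sample comparison with a fixed 30% at one-sided 0.05: about 37 in all.

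**Step 2: power with 35 new patients.** Power = Φ(0.20 / √(0.24/n_new + 0.21/n_old) − z_alpha).

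- 35 vs 130, one-sided 0.05: √(0.24/35 + 0.21/130) = 0.0920; 0.20/0.0920 − 1.645 = 0.53; power **70.1%**. Exact binomial enumeration of the same Wald test gives 71.1%.
- 35 vs 130, one-sided 0.025: 58.4%.
- 35 vs 35 (70 taken literally as a total), one-sided 0.05: 54.7%.
- 35 vs an unlimited historical group, one-sided 0.05: √(0.24/35) = 0.0828; 0.20/0.0828 − 1.645 = 0.77; power 78%. This is the ceiling for 35.

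**Step 3: new-group size that gives 80% against 130.** n_new = 0.24 / [(0.20/2.487)² − 0.21/130] = 49.4, so 50 at one-sided 0.05 (power 80.3%). At one-sided 0.025, 69 are needed, and 50 gives 70.4%.

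**Step 4: can 50 be derived from 35?** The only pre-treatment loss rate in the protocol is the 45% withdrawal in Review and Rationale, and 35/0.55 = 63.6, so 64. A 30% allowance would give 35/0.70 = 50, but the protocol states none.

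**The case against.** **The inference.** The protocol states neither a one-sided alpha nor that 70 is per group. Both are inferred because they reproduce the figure. That is fair, and a reader should not take either as the protocol's own statement. The inference is nevertheless strong, since no two-group variant tried gives 70 as a total. The conclusion also does not depend on it: 35 falls short of 80% on every reading in Step 2, and one-sided 0.05 is the reading most favourable to the protocol.

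**The two targets.** The 35 counts patients who commence, while the 50 is attached to recruitment and treatment. A recruited number may exceed a commencing number, and 50 might serve Aim 2. This stands in part: 35 and 50 are unreconciled rather than proven contradictory. Against it, the Timeframes sentence covers treatment as well as recruitment, and no allowance is stated.

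**The consequence.** A reader might infer that the study will stop at 35 and be underpowered. The documents do not support this. No stopping point at 35 is set, and the operational plan speaks of 50. If 50 do commence, power may be close to 80%.

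**The remedy.** A reader might also infer that 50 simply restores 80%. It does so only at one-sided 0.05, in an unadjusted comparison, with all of about 130 controls usable. As an illustration, 100 usable controls would give Φ(0.20/√(0.24/50 + 0.21/100) − 1.645) = 78%. The planned logistic regression adjusts for covariates including PNPLA3, yet the only genotyped control set described is patients without alcoholic hepatitis. No genotype is stated for the historical controls of Aim 1.

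**Feasibility.** It is tempting to combine about one patient per week with the 45% withdrawal rate and conclude that about 57 (104 × 0.55) would commence in two years. The weekly figure is for patients managed for alcoholic hepatitis, and the 45% is for those referred to the alcohol and drug unit. With no referral or consent rate given, that accrual figure cannot be derived.

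**Conclusion.** The point holds. On the protocol's own inputs, 35 new-protocol patients do not give 80% power. Against about 130 historical controls the power is about 70% at one-sided 0.05 (71% by exact enumeration) and 58% at one-sided 0.025. At one-sided 0.05 the historical group cannot make up the difference however large it is, because the ceiling is 78%.

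The size rests on a true completion rate of 40% against 30%, an unadjusted comparison, and every one of the roughly 130 controls being usable. The last two conditions are favourable to the protocol if controls are lost. If there were no true gain (30% in both groups), power at 35 vs 130 would be about 31% at one-sided 0.05.

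The targets of 35 and 50 are both presented as requirements and are not reconciled. The protocol does not show which one governs, so what is established is a wrong statement about 35, not that the completed study will be underpowered.

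**What to change.** In Sample Size and Statistical or Power Issues:

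- State the sidedness of alpha as an explicit decision.
- Label 70 as per group (140 in total), which matches one-sided 0.05. If one-sided 0.025 is intended, the figure becomes 89 per group.
- Delete the division of 70 by 2.
- Then choose one of two statements. Either keep 35 and give its power against about 130 controls as about 70% (one-sided 0.05). Or take the 50 from Timeframes as the number commencing the new protocol, and say that it gives about 80% only at one-sided 0.05, unadjusted, with all of about 130 controls usable (about 70% at one-sided 0.025).

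Use the same target in Timeframes, and define it the same way in both places, as recruited or as commencing. If 50 is meant as a recruited number, give the allowance that connects it to the number commencing.

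Cost: a few sentences. If 50 already means patients treated, nothing else changes. If it means patients recruited, requiring 50 to commence instead of 35 is 15 more treated patients (15/35 = 43%), and the protocol does not give the rates needed to say how much longer that would take.

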Only a minority of heavy alcohol users develop significant liver disease. Genetic susceptibility likely contributes (Yeluru et al. 2016). The PNPLA3 gene has been reliably associated with non-alcoholic steatohepatitis and hepatitis C induced steatohepatitis (meta-analyses Chamorro et al. 2014; [name], PhD thesis). Recently, the risk (G) allele for PNPLA3 has been associated with AH, with almost double the risk for G allele carriers (Liangpunsakul et al. 2016). Existing studies characterising AH poorly identify alcohol exposure and fail to comprehensively incorporate known or suspected etiological and prognostic factors. Replication and development of this research will inform understanding of risk, treatment prognosis, and tailored behavioural treatment for AH.

AIMS

1. Examine non-inferiority or superiority of a new treatment protocol for patients with Alcoholic Hepatitis (AH) referred to the Alcohol and Drug Assessment Unit by the Department of Gastroenterology and Hepatology.
2. Replicate recent research which has found risk of AH among G allele carriers of PNPLA3.

HYPOTHESES / EXPECTED OUTCOMES

1. We expect that AH patients treated with an updated treatment protocol will have superior outcomes to historical controls of AH patients (Treatment as Usual, TAU).
 - The primary outcome will be treatment engagement and retention.
 - Secondary outcomes will include treatment initiation and drinking behaviours over treatment.
2. Genetic data will better characterize alcohol dependent patients that develop AH, compared to those that do not. The proportion of patients with risk (G) allele for PNPLA3 will be significantly higher among patients with alcoholic hepatitis than historical controls without liver disease.

PROJECT DESIGN

RESEARCH PROJECT SETTING

The research site will be based at the PAH Alcohol and Drug and Alcohol Assessment Unit (ADAU) in the Division of Medicine and Department of Gastroenterology & Hepatology (Dept. G&H).

PARTICIPANTS

RECRUITMENT

Patients are referred to the Dept. G&H for AH from the PAH Emergency Department, other medical/surgical units from other hospitals within and beyond the Metro-South District. Approximately one per week is managed for AH. All consenting patients will be offered the AH CBT program (see Procedure) and comprehensive assessment (see Measures).

ELIGIBILITY CRITERIA

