We include an additional consent provision for DNA to be available for up to 15 years and further research must be first approved by ethics committee. Patients can choose not to consent to this option. Consents will be obtained by [name] (Project manager and treating psychologist).

DATA MANAGEMENT

All data will be kept on secure, password protected, Queensland Health servers. Further access to the specific drive requires Metro South Health administration permissions and approval from the head of this department. Data will be kept consistent with ADAU (and Queensland Health) clinical guidelines, but not less than 7 years. Data used in research will be re-identifiable (coded). The coding "key" will be a password protected excel document stored within the same drive. Management practices will conform to ADAU (and Queensland Health) clinical guidelines, but not less than 7 years. Data will be destroyed via deletion of deidentified electronic file when required. Access to this deidentified data will only be granted to people approved under this application or extension to this application.

Saliva and extracted DNA samples will be stored in a locked freezer in a secure PC2 laboratory at the Queensland University of Technology (QUT). All samples will be de-identified. Laboratory protocol ensures samples are checked for viability routinely. Should a participant withdraw their consent after provision of the saliva sample their sample will be destroyed as per protocol of the PC2 laboratory at the QUT. Any electronic data generated from their sample will be deleted.

DATA ANALYSIS

Aim 1: The primary outcome will be assessed via logistic regression, where the outcome is completed treatment (0 = no, 1 = yes) and the independent variable is treatment group (0 = old protocol, 1 = new protocol). Potential confounding variables will be included as covariates (e.g. dependence severity). As the mechanism of the PNPLA3 gene is unknown it will be included as a covariate. Depending on the distribution of the number of sessions attended, parametric or non-parametric statistics may be employed to determine whether more sessions were attended on average. Again, potential confounding variables will be included as covariates.

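### The primary logistic regression is never linked to the 10-point non-inferiority margin on which the sample size rests, so non-inferiority is left without a test

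*Protocol*

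**What the plan says.** Under Aims, the first aim is "Examine non-inferiority or superiority of a new treatment protocol for patients with Alcoholic Hepatitis (AH" patients. Under Hypotheses / Expected Outcomes, the first hypothesis is superiority: patients on the updated protocol "will have superior outcomes to historical controls of AH patients (Treatment as Usual, TAU").

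Under Sample Size and Statistical or Power Issues, the calculation is for non-inferiority: "when the primary outcome is patient retention non-inferiority requirements were calculated in R version 3.5.0". Its inputs are "Holding power level at 80% and alpha at 0.05", current completion of 30%, and "a modest protocol goal of 40"%. It concludes that 70 patients are "required to support non-inferiority within a 10% equivalence margin". It then halves 70 to 35 new-protocol patients because about 130 historical patients are available. The Timeframes section speaks of 50 required patients.

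Under Data Analysis, Aim 1: "The primary outcome will be assessed via logistic regression, where the outcome is completed treatment (0 = no, 1 = yes"). Treatment group is the independent variable (old = 0, new = 1), with confounders and PNPLA3 as covariates. Neither this section nor the text on secondary outcomes mentions non-inferiority, the margin, a confidence bound, a one-sided level, or a step from the odds ratio to a difference in proportions.

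**The concern.** The sample size is built to exclude a 10-point deficit in the completion proportion. The stated analysis yields a group effect on the log-odds scale, and nothing tells the analyst to set it against that deficit. In its usual use, a logistic group coefficient is tested against no difference, which is a superiority question.

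If so, a result that meets the study's own non-inferiority criterion would be reported only as showing no significant difference. The choice of test would decide the conclusion, so it needs to be fixed before results are seen. There is also a conditional danger: someone might later read a non-significant odds ratio as support for non-inferiority.

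**Working it through.** **Inputs.** From the sample-size section: control completion 30%, new-protocol completion 40%, margin 10 points, power 80%, alpha 0.05 (sidedness not stated), about 130 historical patients, 35 new patients. From Timeframes: 50 new patients. Both group sizes are carried through. All calculations are unadjusted for covariates.

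**Step 1: reproduce the stated 70.** For non-inferiority on the difference in proportions,

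n per arm = (z for 1-alpha + z for power)² × [p0(1-p0) + p1(1-p1)] / (p1 - p0 + margin)².

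With one-sided alpha 0.05: (1.645 + 0.842)² × (0.21 + 0.24) / 0.20² = 6.18 × 0.45 / 0.04 = 69.6, so 70 per arm. One-sided 0.025 gives 89. The stated figure is therefore a risk-difference non-inferiority calculation at one-sided 5%, and the 70 is per arm.

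**Step 2: what a test of no difference would need.** For 30% versus 40%, two-sided 0.05 and 80% power,

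n per arm = [1.96 × √(2 × 0.35 × 0.65) + 0.842 × √0.45]² / 0.10² = (1.322 + 0.565)² / 0.01, which is about 356.

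The two questions differ about fivefold in size (356 / 70).

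**Step 3: power under the planned 30% versus 40%.** Exact enumeration over both binomial distributions, with 130 controls:

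| New patients | Odds ratio against 1 (Wald, two-sided 0.05) | Difference against -10 points (90% CI lower limit) |
|---|---|---|
| 35 | about 20% (20.6%) | about 71% |
| 50 | about 25% | about 81% |

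The large-sample formulas give 20% and 70% for 35 patients, and 25% and 80% for 50.

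**Step 4: where the two readings part.** Take 39/130 controls (30%) and 35 new patients. The standard error of the difference is √(0.21/130 + p(1-p)/35), and the lower limit is the difference minus 1.645 × SE.

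| Completers of 35 | Difference (points) | 90% lower limit (points) | z for log odds ratio |
|---|---|---|---|
| 12 | +4.3 | -10.5 | 0.49 |
| 13 | +7.1 | -7.8 | 0.81 |
| 14 | +10.0 | -5.1 | 1.12 |
| 16 | +15.7 | +0.4 | 1.73 |
| 17 | +18.6 | +3.2 | 2.03 |

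The margin is met from 13 completers; significance against an odds ratio of 1 starts at 17. The planned result, 14/35 = 40%, lies between: odds ratio 1.56 (95% CI 0.72 to 3.37, p = 0.26), but a difference of +10 points (90% CI -5.1 to +25.1), which excludes -10.

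**Step 5: the scale of the margin.** A 10-point deficit from 30% is 20%, an odds ratio of (0.20/0.80)/(0.30/0.70) = 0.583. For control rates of 20% to 40% it runs from 0.44 to 0.64. A margin in percentage points is therefore not one fixed odds ratio, and the conversion has to be specified.

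**Step 6: the conditional error rate.** Suppose the truth sits at the margin, 20% versus 30%, and suppose non-significance were taken as non-inferiority. By exact enumeration, the logistic Wald test is non-significant about 82% of the time with 35 new patients and 74% with 50. The margin test wrongly declares non-inferiority about 4% of the time in both cases.

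**The case against.** The protocol names a model, an outcome coding and a group variable; it states no null hypothesis, p-value rule or confidence level. A reader might infer that the plan commits to testing an odds ratio of 1. That is the default reading of the model, not something the text says.

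A reader might also infer that logistic regression cannot deliver a non-inferiority conclusion. It can: a bound on the odds ratio, or a standardised difference derived from the model, can be compared with a margin, and a significant odds ratio above 1 would itself imply non-inferiority. Nor is the design purely one of non-inferiority. Aim 1 names superiority as well, Hypothesis 1 is superiority, and an ordinary logistic regression answers that directly.

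Finally, a reader might infer that the plan carries a large type I error. The protocol nowhere says that non-significance will be read as non-inferiority, so the 82% and 74% apply only if someone makes that misreading.

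All of this stands, and it limits the wording. The remaining argument, that interval level and testing order belong in an analysis plan not at hand, succeeds only in part. The protocol itself fixes the primary model and contrast, and what it fixes makes no contact with the only hypothesis for which it was sized. An analyst following the section literally would never use the margin.

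**Conclusion.** The point holds in limited form. The sample size rests solely on non-inferiority with a 10-point margin, while the primary analysis is a logistic group effect not linked to that margin. Read in the ordinary way, it serves Hypothesis 1 at about 20% power (35 versus 130) or 25% (50 versus 130) and leaves the non-inferiority half of Aim 1 untested; the margin test would have about 71% or 81%. With 39/130 controls completing, results from 13/35 to 16/35 would change their reported conclusion.

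This rests on four assumptions: the odds ratio is tested against 1 at two-sided 0.05; the margin test is at one-sided 0.05, which reproduces the 70; completion is 30% versus 40%; and there is no covariate adjustment. It should be corrected before analysis, because it concerns the primary outcome and the basis of the design.

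**What to change.** Keep the logistic model and add one paragraph to Data Analysis, Aim 1:

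1. State the non-inferiority hypothesis on the difference in completion proportion, new minus old, with a margin of -10 points.
2. Estimate that difference from the fitted model by standardising over the covariates, with a delta-method or bootstrap confidence interval.
3. Declare non-inferiority if the lower limit of the two-sided 90% interval is above -10 points. State the level explicitly: 90% is an assumption that matches the one-sided 0.05 reproducing the 70. At one-sided 0.025 the interval would be 95% and the same calculation gives 89 per arm.
4. Only if non-inferiority is shown, test superiority: lower limit of the 95% interval above 0.
5. Report the odds ratio as supportive, and say that a non-significant odds ratio is not evidence of non-inferiority.

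A margin prespecified on the odds-ratio scale would also close the gap, but it would need its own justification, since the equivalent of 10 points moves with the control rate. The cost is a paragraph and a few lines of code, with no extra data.

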Tailored CBT Intervention: Shepard et al. (2016) demonstrate that adjunctive telephone-based therapy is a cost-effective modality with good long-term treatment outcomes. As noted, it also meets all of the requirements for a medically unwell, and frequently socially, geographically or mobility challenged AH population. Critical to AH patient abstinence is development of drinking refusal self-efficacy skills, alternative coping strategies, non-pharmacological pain management, modification of situational triggers, nutrition, psychoeducation and management of alcohol craving. The Tailored Alcoholic Hepatitis Intervention will match for the existing generic face-to-face CBT Intervention historical benchmark for length of treatment (3 months) and therapist contact (8 hours). The generic alcohol CBT program has ADAU physician consult plus 8 x 1 hour face-to-face outpatient sessions over 3 months with a clinical psychologist. The Tailored Alcoholic Hepatitis intervention will have a rapid inpatient assessment to enhance treatment engagement consisting of 2 x 20 min sessions while an inpatient, including 1) ADAU Physician assessment and 2) Clinical Psychologist treatment plan. Post discharge, the same clinical psychologist will deliver the intense 2 x weekly 20 min 'booster' telephone sessions for 3 months (totaling 8 hours). Where feasible- based on patient health and geographical location- face-to-face sessions are preferred and can be substituted for telephone sessions.

AIM 2: ASSESSING GENETIC SUSCEPTABILITY TO AH.

We will genotype PNPLA3 in AH patients via saliva sample in the current study. Saliva will be collected from patients via self-collection kit. Patient's spit approximately 2ml saliva into a funnel. Saliva is mixed with a stabilization solution making it suitable for storage. The ADAU maintains a genetically informed database of > 250 treatment seeking, alcohol dependent patients without AH, who will act as our alcohol-exposure adjusted control. Ethics approval for collection and analysis of genetic data of patients attending ADAU has previously been obtained (HREC/14/QPAH/664).

ASSESSMENT AND MEASURES

Assessments are embedded within ADAU routine protocol. They are outlined below:

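### The Aim 1 primary model adjusts for PNPLA3, but the protocol documents no genotype for the historical AH controls, so the comparison could lose some or all of its control group

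*Protocol*

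**What the plan says.** The Aim 1 paragraph of Data Analysis sets out a logistic regression of treatment completion on treatment group, old protocol against new. It allows for confounders in general terms and then makes one firm commitment: "As the mechanism of the PNPLA3 gene is unknown it will be included as a covariate". The comparator is fixed in Hypotheses / Expected Outcomes, which anticipates "superior outcomes to historical controls of AH patients (Treatment as Usual, TAU". The sample size section puts the historical data at about 130 patients.

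Genotype sources appear only in the Aim 2 methods. For AH patients: "We will genotype PNPLA3 in AH patients via saliva sample in the current study". For the comparison group, the unit holds "a genetically informed database of > 250 treatment seeking, alcohol dependent patients without AH". The same paragraph adds: "Ethics approval for collection and analysis of genetic data of patients attending ADAU has previously been obtained".

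Patient Consent gives saliva collection its own information sheet and consent form, and states: "Patients may provide or withdraw consent at any time". Under Data Management, withdrawal leads to destruction of the sample and deletion of the data derived from it.

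**The concern.** A covariate in a regression has to be available in both groups being compared. Here it is documented for the new-protocol arm and for a group that does not enter Aim 1 at all, because those patients do not have AH. For the old-protocol arm it is not documented. If standard software drops records without genotype, the primary analysis could lose part or all of its control group. Collecting saliva from the historical patients afterwards looks difficult, since Review and Rationale reports that over half of AH patients die within a year.

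The reason given for the adjustment, an unknown mechanism, does not make genotype a confounder. Every Aim 1 patient has AH, and the protocol gives no reason why an inherited variant should differ between treatment eras.

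**Working it through.** **1. Who has a documented genotype**

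| Group | Role | Genotype documented? |
|---|---|---|
| New-protocol AH patients | Aim 1, group = 1 | Yes, if they consent to saliva |
| About 130 historical AH patients | Aim 1, group = 0 | No statement |
| More than 250 ADAU patients without AH | Aim 2 controls | Yes, but not in Aim 1 |

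**2. Estimability if no historical AH patient has a genotype**

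- Complete cases: 0 old-protocol patients and at most 35 new-protocol patients (50 if the figure in Timeframes is used). Treatment group equals 1 in every row and coincides with the intercept. The design matrix (intercept, group, PNPLA3) has rank 2 for 3 columns, so there is no treatment coefficient.
- Missing-genotype indicator, with all new-protocol patients genotyped: the indicator equals 1 − group. The matrix has rank 3 for 4 columns, and group is again not identified. If some new-protocol patients lack genotype, the collinearity breaks, but the group effect then rests only on those ungenotyped patients against the controls.
- Imputation: the model could be fitted, but no observed control genotype would exist to check the assumed link between genotype and group. The protocol's only imputation sentence concerns individual trajectories of the drinking outcomes.

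**3. The plan's own sample size**

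Inputs from the sample size section: completion 30% old and 40% new, margin 10 points, power 80%, alpha 0.05 (sidedness not stated).

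n per arm = (z₀.₉₅ + z₀.₈₀)² × [0.3×0.7 + 0.4×0.6] / (0.40 − 0.30 + 0.10)² = (1.645 + 0.842)² × 0.45 / 0.04 ≈ 69.6, so 70.

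The stated 70 reproduces at one-sided 0.05, as a per-arm number. The same level is used below.

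**4. Power if only some controls have genotype**

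Power = Φ(0.20 / SE − 1.645), with SE = √(0.21/n_old + 0.24/n_new). The genotyped shares are assumptions.

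| Controls with genotype (assumed) | n_old | Power, n_new = 35 | Power, n_new = 50 |
|---|---|---|---|
| 100% | 130 | 70% | 80% |
| 50% | 65 | 64% | 72% |
| 25% | 32 | 53% | 59% |
| 10% | 13 | 37% | 40% |
| 0% | 0 | not estimable | not estimable |

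Example, 65 against 35: SE = √(0.00323 + 0.00686) = 0.1004; 0.20/0.1004 = 1.991; 1.991 − 1.645 = 0.346; Φ = 0.64.

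**5. Loss in the new arm as well**

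If 80% of 35 new-protocol patients give saliva (28, assumed) and half of the controls have genotype (65), SE = √(0.00323 + 0.00857) = 0.1086 and power is about 58%.

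**The case against.** A reader might infer that the controls will certainly drop out and that the treatment effect cannot be estimated. The documents do not go that far, for two reasons. First, the earlier ethics approval covers genetic data from patients attending ADAU and is not limited to those without AH, so some historical AH patients may have been sampled. The description of the database as patients without AH identifies the Aim 2 controls; it does not say that no AH patient was ever genotyped. Second, non-estimability presumes that incomplete records are dropped. The protocol gives no rule for missing covariates in this model, and such a rule may properly sit in an SAP that is not shown. Both points stand and limit the claim. Neither supplies the missing genotypes, and neither makes imputing an entire arm a sound basis for a primary analysis.

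The power figures are also open to challenge. They rest on assumed shares, a one-sided level that the protocol does not state, and an unadjusted risk difference in place of an adjusted logistic model. The 70% starting point is already below the planned 80% because the per-arm 70 was halved to 35, which is a separate matter, as is the mismatch with the 50 patients named in Timeframes. The figures therefore show direction and rough size only.

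Finally, the protocol hopes that the genetic work will inform prognosis, and adjusting for a prognostic factor in a non-randomised comparison can be reasonable. That supports a secondary analysis. It does not justify tying the primary model to a variable not documented in one arm.

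**Conclusion.** The point holds in this form: the protocol commits its primary Aim 1 model to a covariate that it documents for the new arm but not for the comparator. If no historical AH patient was genotyped and incomplete records are dropped, no control remains and there is no treatment estimate. If a share was genotyped, the comparison survives with fewer controls. On the stated assumptions with 35 new-protocol patients, power goes from 70% to about 64% at half and about 53% at a quarter, and lower again if new-protocol patients decline or withdraw saliva consent.

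The defect is confined to this one covariate: without PNPLA3, the model keeps all of the roughly 130 controls and the effect is estimable. A reader might also extend the point to the analysis of sessions attended, but PNPLA3 is named before that analysis, which refers only to potential confounders in general. The documents do not clearly place PNPLA3 there.

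**What to change.** - Remove PNPLA3 from the Aim 1 primary model, and make clear that it is not a required covariate in the sessions analysis.
- Adjust the primary model only for baseline covariates confirmed to be recorded in both eras. Dependence severity is a candidate. MELD should be used only if the historical records hold it, which the protocol does not say.
- Report the association of PNPLA3 with completion as an exploratory analysis in genotyped patients.
- If historical AH genotypes exist, state how many, and use PNPLA3 adjustment only as a sensitivity analysis.

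The cost is one sentence deleted, a short replacement and a check of the historical records; no new data are needed. What is given up is genotype adjustment in the primary model, for which the protocol offers no confounding rationale.
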